2.1.3 Subgroup of interest

No subgroup is defined.

2.2 Participant disposition, demographics and other baseline characteristics

Data for background and demographic variables will be summarized by treatment arm based on the FAS. Continuous variables will be presented with mean, median, 25th percentile, 75th percentile, standard deviation, minimum, maximum, and the number of non-missing observations. Categorical data will be displayed via absolute and relative frequencies for each category (including a category labelled "missing" when appropriate).

The following demographics and baseline characteristics will be reported by treatment arm:

Recipient demographics: age, age group (< 60 years and ≥ 60 years), gender, race (Asian, White, Black or African American, American Indian or Alaska Native, Native Hawaiian or Other Pacific Islander, and Other), height, weight, body mass index (BMI), and region (North America, Europe, and Rest of the world).

- Recipient baseline characteristics: HbA1c level at the time of transplantation, renal function measured by eGFR (MDRD4) (< 30, [30, 55), [55, 70), [70, 90), and ≥ 90 mL/min/1.73m²), diabetic status* (Y/N) prior to transplantation, HCV status (pos/neg), ratio of spot urine protein to creatinine categories**, and evidence and treatment of HCC prior to transplantation (Y/N).
- Donor background information: age, gender, race, weight, allograft weight, donor characteristics (standard criteria donor (SCD), expanded criteria (EXD)), donor category (deceased heart beating, deceased non heart beating), cause of death, ABO blood group/type, RH type, and hypotension prior to procurement (Y/N/unknown).
- Recipient liver transplant background information: end stage disease leading to transplantation, MELD score summary and by-category (≤ 14,[15, 19], [20, 24], [25, 29], and ≥ 30), UNOS classification (Status 1A, Status1B, and Status Non 1), CHILD classification (Status A, Status B, and Status C), and ABO match (Identical and Compatible).
- Recipient and donor viral serology for: CMV, EBV, HCV, HBsAg Anti-Hep B Surface, Anti-Hep B Core, and HIV. CMV donor/recipient constellation (D+R+ / D-R- / D+R- / DR+) is included.
- Liver transplantation procedure information: cold ischemia time summary and by category (≤ 6, (6, 12], and > 12 hours).

* A patient is identified as not having diabetes prior to transplantation if all of the following are true:

- 1. Diabetes was not included in the medical history.
- 2. Glucose (random) < 11.1 mmol/L (200 mg/dL) at the time of transplantation.
- 3. Diabetes was not recorded as reason for any medication given prior to transplantation.
- 4. HbA1c < 5.7% at the time of transplantation.
- 5. If any of the above criteria is unknown (e.g., lab values), the participant will be considered to have no diabetes pre-transplant if all other criteria are true.

** Ratio of spot urine protein to creatinine will be categorized as < 30 mg/g, [30, 500) mg/g, [500, 1000) mg/g, [1000, 3000) mg/g, and $\geq 3000 \text{ mg/g}$.

For variables which are collected multiple times before transplantation, the last available values on or prior to transplantation will be used for summary if not specified otherwise.

Demographics, baseline characteristics, and recipient liver transplant background information, will be provided in the listings.

2.2.1 Medical history

Relevant medical history/current medical conditions will be summarized by primary system organ class, preferred term, and treatment arm. Frequencies and percentages of participants in the FAS in each treatment arm will be presented.

Relevant ongoing medical history/current medical conditions data will be listed.

. .

2.2.2 Participant disposition

The number and percentage of participants who prematurely discontinued from study medication and from study (by primary reasons), and who completed treatment periods (12-month and 24-month), respectively and cumulatively, will be provided by treatment based on the FAS.

A listing of participant disposition and randomization information and a listing of primary reasons and date/study day for premature discontinuation of the randomized study treatment will be provided. Discontinuation of study medication reasons are from Disposition CRFs.

2.3 Treatments (study treatment, rescue medication, concomitant therapies, compliance)

The SAF will be used for the analyses below. All study treatment summaries will be presented by treatment arm. Categorical data will be summarized as frequencies and percentages. For continuous data, n, mean, standard deviation, median, 25^{th} and 75^{th} percentiles, minimum, and maximum will be presented.

The average daily dose of each study drug (CFZ533, TAC, and MMF) will be presented by treatment and by visit window from baseline. In calculating average dose, zero daily dose will be used for periods of temporary interruption.

Corticosteroids dosage

The average daily dose and the daily body weight-adjusted prednisone equivalent dosages [mg/kg/day] will be summarized using descriptive statistics by treatment. Steroids administered after the discontinuation of randomized study medication will be ignored. To adjust the dose, the body weight measured closest to the start of a steroid dose will be used.

The averages will only include corticosteroids given for "Rejection prophylaxis" purpose. Steroids (p.o. or i.v.) used for the treatment of rejection episodes will be presented separately. Inhaled, intra-nasal, and topical corticosteroids will not be included in either analysis.

For conversion factors to prednisone equivalent dosages see Table 5-8.

2.3.2 Prior, concomitant and post therapies

Prior/concomitant therapies will be summarized based on the SAF.

All medications recorded on the concomitant medications and significant non-drug therapies eCRF page will be classified as *prior* or *concomitant* medications and grouped by Anatomical Therapeutic Classification (ATC) codes and preferred terms (PT). Number and percentage of participants using each medication (by ATC and PT) will be presented by treatment.

Prior medications will be drugs taken prior to the start of study treatment regardless of whether they continue thereafter; any medication given at least once between the start and the end of study treatment was a concomitant medication, including those started before randomization and continued into the treatment period. The start and the end of study treatment is defined in Section 2.1.1.

Immunosuppressive therapies taken after discontinuation of study drug will be summarized separately from study drug therapies. Immunosuppressive therapies are defined as by the investigator in the CRF.

Rules for imputing incomplete dates are described in Section 5.2.

2.4 Analysis of the primary objective

The primary objective is to evaluate the rate of composite efficacy failure (BPAR, graft loss, or death) with CFZ533 600 mg and 300 mg Q2W maintenance regimen compared to TAC Control at Month 12 post-transplantation. Analysis will be on the FAS.

The analysis of the primary objective has been modified due to the early termination of the study.

2.4.1 Primary endpoint

The primary efficacy endpoint is occurrence of composite efficacy failure (BPAR, graft loss, or death) at 12 months post-transplantation based on central pathologist evaluation (graft loss and death will be from local evaluation). The estimand is:

- Population: defined through appropriate inclusion/exclusion criteria to reflect the targeted population.
- Endpoint: composite efficacy failure at Month 12 post-transplantation, defined as BPAR, graft loss, or death.
- Treatment of interest: the randomized treatment, CFZ533 300 mg + MMF, CFZ533 600 mg + MMF, and TAC+MMF, regardless of treatment or study discontinuation, loss to follow-up, ascites-based dosing adjustment, or administration of CS (treatment policy).
- Summary measure: the difference in the proportion of participants with composite efficacy failure in CFZ533 arms at 12 months post-transplantation as compared to control.

BPAR is defined as an acute rejection confirmed by biopsy within 48 hours of the suspected rejection (preferably within 24 hours) with a rejection activity index (RAI) score \geq 3. Events of rejection which were discovered incidentally during the study (e.g., via optional Month 12 biopsy or standard of care biopsy) with no clinical suspicion of acute rejection will not be included in the assessment of the primary endpoint. Note that ascites-based dosing adjustment is not considered a rescue medication because the occurrence of ascites is not due to lack of efficacy. Accordingly, administering CFZ533 to compensate drug loss caused by ascites cannot be considered rescue medication. In addition, this unscheduled administration aims not to result in exposure higher than that seen in participants with no ascites.

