6.6.2 Recommended treatment of adverse events

Acute rejection

For all acute rejection episodes, regardless of initiation of anti-rejection treatment, an allograft biopsy must be performed preferably within 24 hours, latest within 48 hours. Whenever possible, anti-rejection therapy should be postponed until a histological diagnosis of rejection is confirmed. These biopsies will be read by the local pathologist (as well as a central reader up to Month 24 visit), and the histological lesions will be graded according to the Banff criteria (Appendix 3). Determination of the need for treatment will be according to the local pathologist's findings and the investigator's judgement.

All episodes of acute rejection should be treated as per local practice, using for example bolus steroids, increased dose of oral steroids or tacrolimus (for control participants) as first line and anti-T-cell antibody for steroid-resistant rejections.

A steroid-resistant acute rejection episode will be defined when no stabilization and/or no improvement of liver enzymes is seen within five days after initiation of methylprednisolone, when the participant has received at least 3 bolus injections with a minimum of 500 mg/bolus, or a total of 1.5 g of methylprednisolone, or initiation of anti-T-cell antibody treatment after repetitive methylprednisolone.

Whenever possible a re-biopsy should be performed to confirm an ongoing steroid-resistant acute rejection prior to initiating anti-T-cell antibody treatment.

The specific anti-rejection treatment, corticosteroids and anti-T-cell antibody treatment must be recorded on the appropriate CRFs. Increased doses of tacrolimus applied as anti-rejection treatment will be recorded on the corresponding dose administration record CRF page

Participants requiring cyclosporine, azathioprine, everolimus, sirolimus or tacrolimus (if the participant is on a CFZ533 arm) or any other agents for anti-rejection treatment will be discontinued from the randomized study treatment but will be followed until Month 24. Any participant requiring anti-T cell antibody therapy for rejection up to Month 24 should be discontinued from CFZ533 but should continue in the study on standard of care immunosuppression. Participants requiring any of the above treatments for rejection during the extension will be discontinued from the study.

The CFZ533 dose will not be modified and no extra dosing will be administered following a rejection episode.

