8.3 Efficacy

8.3.1 Suspected Acute Rejection/Biopsy Proven Acute Rejection (BPAR)

All episodes of acute rejection must be recorded on the appropriate CRF. Recording should be done within 24 h of occurrence, to ensure timely information sharing to the DMC. The precise reason for suspicion of an acute rejection and the final diagnosis (either to confirm or rule out the diagnosis of acute rejection) and all anti-rejection therapy administered must be recorded.

A biopsy proven acute rejection (BPAR) is defined as an acute rejection confirmed by biopsy with a rejection activity index (RAI) score \geq 3, Appendix 3. For all suspected rejection episodes, a liver biopsy must be performed preferably within 24 hours, latest within 48 hours whenever clinically possible, regardless of initiation of anti-rejection treatment.

The liver biopsies will be read by a local pathologist according to the Banff criteria (Appendix 3) and will be used to guide participant management. The results of the biopsy read by the local pathologist must be recorded on the appropriate CRF.

In addition, up to Month 24 visit completion, biopsy specimen slides from these for "cause biopsies" will be sent to an independent central pathologist for blinded review. The efficacy analysis will rely on the central pathologist's evaluations and will be based on acute rejection confirmed by a biopsy. Central laboratory chemistry tests should be performed at the time of suspected BPAR and thereafter until the final clinical outcome. Lactate dehydrogenase (LDH) test results, if available locally, should also be captured in the eCRF

Every suspected acute rejection event must be recorded on the appropriate CRF with full details including whether or not a liver biopsy was performed (if not, reason should be provided, e.g. abnormal coagulation test) and the primary clinical diagnosis.

Suspected acute rejection episodes ultimately diagnosed to be other conditions should also be recorded with the final diagnosis on the appropriate CRF.

For any diagnosis of acute rejection, the treatment given and the final clinical outcome of the event must be recorded on the appropriate CRF.

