Details about the definition of efficacy and safety events, data handling conventions including "re-aligned" visit windows, imputation of missing dates, and other details about study concepts and terms can be found in Section 5. Note that the visits defined in the protocol are used to guide investigators whereas the "re-aligned" visit windows (Table 5-1) (simply referred to as visit windows hereafter) will be used for the analyses.

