5.4.1 Efficacy endpoint derivations based on central readings

Humoral rejection/AMR

A rejection is considered as a humoral rejection if:

- MI.MITEST = "AAMR" and MI.MIRESC = "Y"; AND
- Reason for biopsy = "Suspicion of rejection" on Liver Allograft Biopsy eCRF page.

Date of AMR will be MI.MIDAT_RAW when MI.MITEST = "AAMR" and MI. MIRESC= "Y".

AR

A rejection is considered an AR if:

- Antibody-mediated rejection (see above); **OR**
- MI.MITEST = "ATCELL" and MI. MIRESC = "Y"; AND
- Reason for biopsy = "Suspicion of rejection" on Liver Allograft Biopsy eCRF page.

Date of AR will be min(MI.MIDAT_RAW when MI.MITEST = "AAMR", MI.MIDAT_RAW when MI.MITEST = "ATCELL") when MI. MIRESC= "Y".

BPAR

A rejection is considered a BPAR if:

- AR (see above); AND
- MI.MITEST = "RAITOT" and MI.MIRESN \geq 3; AND
- Reason for biopsy = "Suspicion of rejection" on Liver Allograft Biopsy eCRF page.

Date of BPAR will be date of MI.MIDAT_RAW when MI.MITEST = "RAITOT" and MI.MIRESN \geq 3.

Steroid resistant AR

A rejection is considered a steroid resistant AR if

- AR (see above); AND
- Was the rejection steroid resistant = "Yes" from Liver Allograft Rejection eCRF page Date of steroid resistant AR will be the date of AR (see above).

Antibody treated AR

A rejection is considered an antibody treated AR if

- AR (see above); AND
- Was antibody treatment administered = "Yes" from Liver Allograft Rejection eCRF page

Date of antibody treated AR will be the date of AR (see above).

Steroid treated AR

A rejection is considered an steroid treated AR if

- AR (see above); AND
- Were steroids administered = "Yes" from Liver Allograft Rejection eCRF page

Date of steroid treated AR will be the date of AR (see above).

Steroid resistant BPAR

A rejection is considered a steroid resistant BPAR if

- BPAR (see above); AND
- Was the rejection steroid resistant = "Yes" from Liver Allograft Rejection eCRF page Date of steroid resistant BPAR will be the date of BPAR (see above).

Antibody treated BPAR

A rejection is considered an antibody treated BPAR if

- BPAR (see above); AND
- Was antibody treatment administered = "Yes" from Liver Allograft Rejection eCRF page

Date of antibody treated BPAR will be the date of BPAR (see above).

Steroid treated BPAR

A rejection is considered an steroid treated BPAR if

- BPAR (see above); AND
- Were steroids administered = "Yes" from Liver Allograft Rejection eCRF page

Date of steroid treated BPAR will be the date of BPAR (see above).

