5.4.2 Efficacy endpoint derivations based on local readings

AR

A rejection is considered an AR if:

• Primary clinical diagnosis = "Acute rejection" or "Acute and chronic rejection from Liver Allograft Rejection eCRF page.

Date of AR will be "date rejection was first suspected" from the Liver Allograft Rejection eCRF, or if missing, the first available date of the biopsy of the particular rejection episode from the Liver Allograft Biopsy eCRF page.

Treated AR (tAR)

A rejection is considered a tAR if:

- Acute rejection (see above); AND
- Was anti-rejection therapy administered = "yes" from Liver Allograft Rejection eCRF page

Date of tAR will be the date of the corresponding AR (note: tAR is the subset of AR).

BPAR

A rejection is considered a BPAR if:

- Histological Evidence of Acute Rejection = "Yes" and of Acute and Chronic Rejection = "Yes" from Liver Allograft Biopsy eCRF page; AND
- Total RAI score ≥ 3 and Reason for biopsy = "Suspicion of rejection" from Liver Allograft Biopsy eCRF page.

Date of BPAR will be the date of the corresponding AR (note: BPAR is a subset of AR).

Treated BPAR (tBPAR)

A rejection is considered a tBPAR if:

- Biopsy-proven acute rejection (BPAR) (see above) AND
- Was anti-rejection therapy administered = "yes" from Liver Allograft Rejection eCRF page

Date of tBPAR will be the date of the corresponding AR (note: tBPAR is the subset of AR).

Death

Death will be recorded at either Study Completion, Follow-up, or as the outcome of an AE/Infection, if it occurs.

The date of Death will be the date of death recorded on the Disposition eCRF.

Graft loss

The allograft will be presumed to be lost on the day the participant becomes newly listed for a liver allograft or the day the participant is re-transplanted or dies due to liver failure.

Graft losses will be identified from Graft Loss CRF page.

Loss to follow-up

A lost-to-follow-up participant is one who discontinued the study and did not experience BPAR, graft loss, or death, and whose last day of contact is prior to the day of the lower limit of the (Month 12 or 24) visit window. The date of loss to follow-up is the last contact date.

Composite efficacy failure

The date of composite efficacy failure will be the earliest non-missing date among the individual components of the composite endpoint.

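### SAP 2.4.1 puts a 48-hour biopsy limit inside the BPAR definition for the primary endpoint; the protocol's definition and the SAP's own derivation have none

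*SAP*

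**What the plan says.** SAP 2.4.1, which defines the primary endpoint, states: "BPAR is defined as an acute rejection confirmed by biopsy within 48 hours of the suspected rejection (preferably within 24 hours", and adds RAI of at least 3. Its next sentence excludes rejections found incidentally, without clinical suspicion.

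Protocol 8.3.1 says BPAR "is defined as an acute rejection confirmed by biopsy with a rejection activity index (RAI) score" of at least 3. The time limit comes in a separate sentence on conduct: "latest within 48 hours whenever clinically possible, regardless of initiation of anti-rejection treatment". Protocol 6.6.2 repeats it as conduct: "an allograft biopsy must be performed preferably within 24 hours, latest within 48 hours". The endpoint tables (protocol Table 2-1, SAP Table 1-1) give only RAI of at least 3.

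SAP 2.1 says where event rules are to be found: "Details about the definition of efficacy and safety events, data handling conventions including" visit windows are in Section 5. The central BPAR rule in SAP 5.4.1 needs an acute rejection, a total RAI of at least 3 and suspicion of rejection as the reason for biopsy. It fixes the date ("Date of BPAR will be date of MI.MIDAT_RAW when MI.MITEST" meets the RAI condition) and checks no interval.

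Two further passages concern the local reading. The local BPAR rule in SAP 5.4.2 requires "Histological Evidence of Acute Rejection = 'Yes' and of Acute and Chronic Rejection = 'Yes' from Liver Allograft Biopsy eCRF page". SAP 2.1.1 restricts efficacy analyses to centrally adjudicated data, while SAP 5.4 and protocol 12.4.1 use the local reading when the central one is missing.

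**The concern.** The narrative definition and the programmable rule for one component of the primary endpoint disagree. Protocol 8.3.1 qualifies its 48 hours by clinical feasibility, so it foresees later biopsies, and the disagreement covers cases that can occur. A programmer who goes to Section 5 counts such a rejection. A reader of 2.4.1 would believe it was excluded. The limit can remove only BPARs, never graft losses or deaths.

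The local BPAR rule, read literally, needs both histology items to be positive, so purely acute rejection would fail it. The local acute rejection rule in the same section joins its two diagnoses with 'or'. The central-only statement in 2.1.1 would leave a participant with no central reading without any BPAR assessment.

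**Working it through.** **1. The rules side by side**

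| Place | Condition for BPAR | Time limit |
|---|---|---|
| Protocol 8.3.1 (definition) | biopsy-confirmed, RAI ≥ 3 | none |
| Protocol Table 2-1, SAP Table 1-1 | RAI ≥ 3 | none |
| SAP 2.4.1 | biopsy-confirmed, RAI ≥ 3, clinically suspected | 48 hours from suspicion |
| SAP 5.4.1 (central) | acute rejection, RAI ≥ 3, biopsied for suspicion | none |
| SAP 5.4.2 (local) | both histology items, RAI ≥ 3, biopsied for suspicion | none |

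Take a for-cause biopsy four days after suspicion, read centrally with RAI ≥ 3. It is an event in every row except SAP 2.4.1 and, if the finding is purely acute, the literal local rule.

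**2. The plan's own figures**

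With Beta(1/3, 1/3) priors, binomial counts, and 48 v 32 participants, all 15 probabilities of success in SAP Table 3-2 reproduce to within 0.002 (for example 0.904 at 0.11 v 0.103). The design figures are not in dispute.

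**3. What one event does under SAP 2.4.2**

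Inputs: prior Gamma(0.001, 0.001), margin 0.15 and threshold 0.8 (SAP 2.4.2); 48 and 32 participants (SAP 3.2). Follow-up is capped at Day 358 for Month 12 analyses (SAP 5.1). From Day 1 that is 357/365.25 = 0.977 year. Giving every participant this maximum (an assumption), t = 48 × 0.977 = 46.9 and 32 × 0.977 = 31.3 years.

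Formulas: λ | data ~ Gamma(0.001 + y, 0.001 + t); θ = 1 − exp(−λ); success if P(θ_CFZ533 − θ_control < 0.15 | data) > 0.8.

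| Events, CFZ533 v control | P | Result |
|---|---|---|
| 10 v 3 | 0.758 | fail |
| 9 v 3 | 0.833 | success |
| 9 v 2 | 0.724 | fail |
| 5 v 3 (close to 10% in each arm) | 0.987 | success |

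Dropping one CFZ533 event turns 10 v 3 into a success. Dropping one control event turns 9 v 3 into a failure. Near the planned rates one event changes nothing. With 0.8 year each, the boundary at 3 control events lies between 8 (0.816, success) and 9 (0.735, fail).

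**4. Chance of success if late BPARs were dropped**

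The documents give neither BPAR's share of failures (s) nor the share of BPARs biopsied late (l). Assume s of 50%, 70% or 90%, and l of 10%, 20% or 30%, equal in both arms. Each true rate is multiplied by 1 − s·l and counts are binomial. At s = 90% and l = 30% the factor is 1 − 0.27 = 0.73, so 25% v 10% becomes 18.25% v 7.3%.

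| True rates | No limit | s = 50% | s = 70% | s = 90% |
|---|---|---|---|---|
| 25% v 10% | 28% | 31/34/38% | 32/37/43% | 34/41/48% |
| 10% v 10% | 95% | 95/96/96% | 95/96/97% | 96/96/97% |

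Entries are for l = 10/20/30%, at 0.977 year each. With 0.8 year and s = 70% they are 17% rising to 20/24/28%, and 88% rising to 89/90/92%.

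**5. Direction**

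Unequal losses can push either way. Under the planned binomial rule at 15% v 10%, the chance of success is 0.718. It becomes 0.795 if only CFZ533 loses 10% of its failures and 0.680 if only control does.

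**The case against.** The strongest reply is that the documents largely settle the matter. Section 5 is the stated home of event definitions, 5.4.1 is complete without an interval, and the phrase in 2.4.1 closely tracks the protocol's biopsy instruction. Its 24-hour preference cannot be a yes/no criterion. On the likeliest reading it is carried-over conduct wording and no count changes. This stands as a statement about programming. It does not remove the conflict: 2.4.1 presents the phrase as part of a definition, and its next sentence, on incidental findings, is a real counting rule that 5.4.1 implements through the reason for biopsy. Nothing tells the reader that one counts and the other does not. SAP 2.1 and 2.4 warn that analyses were modified after early termination, but neither names a 48-hour criterion, and a general warning cannot reconcile two sections of one SAP.

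A reader might infer an undisclosed change of endpoint because SAP Section 4 lists no changes. That is weak evidence: Section 4 is equally silent on the move from a binomial to a Poisson primary analysis.

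It is also fair that the shifts in chance of success rest on assumptions. With equal late shares they are upper bounds, because a participant with a late-biopsied BPAR may still fail through a timely BPAR, graft loss or death. On the local rule, the two 'and'/'or' conditions use different CRF fields and the CRF is not in the documents, so whether both histology items can be positive together is unknown.

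**Conclusion.** The textual conflict is certain; its effect on the result is unknown and may be nil. SAP 2.4.1 gives one definition of BPAR, and protocol 8.3.1 and SAP 5.4.1 give another. The likeliest harm is an abbreviated study report whose stated endpoint differs from the one computed.

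A reader might go further and infer that late rejections will be dropped, or that the wording favours CFZ533. The documents support neither. They report no late biopsy, they point programming to 5.4.1, and the direction depends on which arm loses events. Nor does a development decision turn on this, since SAP Section 1 records that the study was terminated after the interim analysis.

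If the limit were applied, one event would decide only near the boundary. With equal late shares and maximum follow-up, the chance of success would rise from about 28% to at most about 48% at true rates of 25% v 10%, and from about 95% to at most about 97% at 10% v 10%. These figures rest on the assumed exposure, BPAR share and late share.

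The local 'and' and the central-only wording touch the primary endpoint only when the central reading is missing. Severity: minor.

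**What to change.** - SAP 2.4.1: delete the 48-hour and 24-hour phrase from the BPAR definition so that it matches protocol 8.3.1 and SAP 5.4.1. The protocol's instruction on when to biopsy stays as it is.
- SAP 5.4.2: let either histology item satisfy the local BPAR rule, after checking the CRF.
- SAP 2.1, 2.1.1 and 2.4.1: state that the local reading is used when the central one is missing. Editing 2.1.1 alone would leave central-only wording in the other two.
- If the 48-hour limit is intended: add it to 5.4.1, list it in Section 4, and show the primary result with and without it. The derivations name dates only (for suspicion: "Date of AR will be 'date rejection was first suspected' from the Liver Allograft Rejection eCRF"), so the rule would have to be written in whole days unless clock times are collected.

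The cost is a few wording edits and no new data. A rerun is needed only if programming followed 2.4.1 or the literal 'and'. If the limit is kept, add one Section 4 entry and one extra run of the primary analysis.
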